2. ABBREVIATIONS

AE – adverse event

CCTO – Cancer Clinical Trials Office

CFR – Code of Federal Regulations

CRA – clinical research associate

CRF – case report form

CTCAE – Common Terminology Criteria for Adverse Events

FDA – Food and Drug Administration

GCP – good clinical practice

IRB – Institutional Review Board

IV – intravenously

mg – milligram

ml - milliliter

PI – principal investigator

PRMC – Protocol Review And Monitoring Committee

RSC – Research Support Center

SAE – serious adverse event

UAMS - University of Arkansas for Medical Sciences

UPIRTSO/UPR – unanticipated problems involving risk to subjects or others

3. **PROTOCOL SUMMARY**

Primary Objective: To determine if Fluorescein systemic injection during hysterectomy procedure can be useful in revealing the depth of endometrial cancer invasion.

Secondary Objectives: To compare depth of invasion as detected with fluorescein to that detected by frozen section and final pathology.

Exploratory Objectives: Can systemic fluorescein injection at time of hysterectomy provide an inexpensive and rapid determination of endometrial cancer invasion into the myometrium.

Study Population: Women with endometrial cancer who are undergoing hysterectomy.

Inclusion Criteria:

1. Known endometrial cancer and scheduled for hysterectomy as part of their treatment.
2. No known allergy to fluorescein dye.
3. Ability to understand and sign informed consent.
4. 18 year of age or older

Exclusion Criteria:

1. Prior hysterectomy.
2. Known sensitivity to fluorescein dye.

Investigational Product: Fluorescein dye injected systemically

Study Design: Pilot

4. **STUDY SCHEMA**

100 women with endometrial cancer who are scheduled for a hysterectomy as a part of their initial treatment

Intravenous injection of 1 ampule (5 cc) of fluorescein dye prior to ligation of the uterine arteries during hysterectomy

Uterus sent immediately to surgical pathology for opening, cross-sectioning, and exposure with Woods lamp to determine depth of invasion of endometrial cancer into the myometrium. Photograph taken of representative area and frozen section performed at same area

Comparison of final pathology depth of invasion with frozen section depth of invasion and fluorescein dye detected depth of invasion to determine accuracy of procedure.

5. BACKGROUND

Endometrial cancer is a surgically staged disease. Staging involves removal of the uterus, tubes and ovaries as well as lymph nodes in the pelvic and aortic regions. In women with cancer that does not invade the uterine muscle or is of low grade and invades less than 50% of the muscle, removal of the lymph nodes is not mandatory. Intraoperative evaluation of the depth of invasion of the cancer is critical, therefore, in determining which patients require lymphadenectomy. Gross visualization is highly inaccurate. It is more sensitive to obtain a pathological frozen section on the uterus to accurately diagnose depth of invasion. However, frozen section increases the operative time and incurs an additional expense for the procedure. A rapid and accurate intraoperative assessment of invasion which could be performed in the operating room would reduce the time and expense of a frozen section. We propose to utilize fluorescein dye given intravenously prior to the hysterectomy to aid in visually determining the depth of invasion. If this assessment correlates well with the pathologic depth of invasion, then this could represent a valuable intraoperative tool to determine which patients require lymphadenectomy.

Fluorescein is approved by the FDA for angiography of the retinal vessels. There are many procedures that utilize fluorescein beyond its FDA indication. It is commonly used during surgery to assess the vascular viability of tissue, most particularly the viability of the intestines when there is concern. In this situation, fluorescein is injected intravenously and the intestines are examined using a Woods lamp to detect the areas of fluorescence. Areas of poor vascularity will not fluoresce. It is also commonly used to detect the boundaries of skin lesions. For example, in assessment of vulvar Paget's disease fluorescein injection and visualization of the vulva with Woods lamp can detect the extent of the lesion that would otherwise not be detectable by the naked eye.

6. TRIAL OBJECTIVES

- a. **Primary Objective:** To determine if Fluorescein systemic injection during hysterectomy procedure can be useful in revealing the depth of endometrial cancer invasion
- b. **Secondary Objectives:** To compare depth of invasion as detected with fluorescein to that detected by frozen section and final pathology
- c. **Exploratory Objectives:** Can systemic fluorescein injection at time of hysterectomy provide an inexpensive and rapid determination of endometrial cancer invasion into the myometrium

7. PATIENT POPULATION

Women with documented endometrial cancer who are scheduled for a hysterectomy as part of their initial cancer staging.

Eligibility Criteria: Subjects are eligible for the study if the following inclusion and exclusion criteria are met:

Inclusion Criteria:

1. Documented endometrial cancer and scheduled for hysterectomy as part of their treatment.
2. No known allergy to fluorescein dye
3. Ability to understand and sign informed consent
4. 18 year of age or older

Exclusion Criteria:

1. Prior hysterectomy
2. Known sensitivity to fluorescein dye

8. INVESTIGATIONAL AGENT – Fluorescein dye for intravenous injection

- a. General Description:** Fluorescein is a synthetic organic compound with a dark orange color that is dissolved in water. It is supplied in a glass ampule with 500 mg of fluorescein sodium in 5 mL of water. The dye is injected intravenously and is stimulated by blue light (Woods lamp) in the range of 465 to 490 nm. Under the blue light, it will fluoresce as a bright yellow-green color.
- b. Manufacturing and Formulation:** Fluorescein 500mg/5mL is a sterile solution containing fluorescein sodium for intravenous injection. It is manufactured by multiple companies including Alcon Chemical (Fluorescite). Each 1.0 mL of solution contains 100 mg fluorescein sodium. One ampoule of 5mL contains 500 mg fluorescein sodium.
Excipients: Sodium hydroxide for pH adjustment, water for injections.
- c. Preparation:** Comes packaged as a single ampule containing 5 cc of fluorescein dye.
- d. Dosing Administration or Utilization:** One ampule (5 cc) injected intravenously prior to ligation of the uterine arteries.
- e. Storage and Disposition:** Fluorescein ampules should be stored between 5°C to 25°C.
- f. Label Information:** See Appendix I: Manufacturer's label
- g. Agent Ordering:** Fluorescein dye will be purchased by Pharmacy for this study, and the Division of Gynecologic Oncology will reimburse pharmacy as subjects complete the study.
- h. Agent Accountability:** UAMS Pharmacy Department

9. TREATMENT PLAN

a. On-Study Evaluation:

After signing the IRB-approved informed consent form, research participants will be registered by a clinical research associate (CRA) in the Cancer Clinical Trials Office (CCTO). Upon registration, surgery will be scheduled at the next available surgery time slot. All research participants will receive fluorescein injection through their existing intravenous line during their operative procedure for endometrial cancer staging. This will consist of one ampule (5 cc) injected intravenously prior to ligation of the uterine arteries. After the uterus is removed it will be sent to surgical pathology for evaluation as per routine care. The pathologist will open the uterus and evaluate the endometrium. He or she will then cut into the myometrium in an area most suspicious for invasion. The cross section of the myometrium and endometrium will be photographed while exposed to a Woods lamp. The normal myometrium will have a yellow fluorescent appearance under the Woods lamp. The cancerous tissue will have minimal fluorescence. The measurement will be taken estimating the depth of invasion of the cancer into the myometrium on the basis of its physical appearance under the Woods lamp. Cross-sectioning of the uterus is routine procedure by pathology for the intra-operative evaluation of endometrial cancer. This information routinely is provided in order to determine if lymph node staging is necessary.

The area that was measured and photographed will then be prepared for a frozen section to document depth of invasion. This is the standard procedure performed during an endometrial staging. The depth of invasion on the frozen section will be recorded. This same area will undergo histologic confirmation by permanent pathology to determine depth of invasion. The frozen section is part of routine standard of care in evaluation of endometrial cancer.

Subjects will be informed prior to participation in this study that they will have a bright yellow discoloration of their urine and possibly a mild yellow discoloration of their skin for up to 24 hours after the procedure.

b. Dose Assignment: This is a single arm study. A single dose of Fluorescein will be administered to all subjects in this study.

c. Specimen Handling: The uterus will be sent to pathology immediately after its removal from the patient. The study pathologist will be informed when to expect a subject specimen and will prepare the lab for Woods lamp evaluation, measurement and photography. The remainder of the specimens from the procedure will be processed in the usual manner for routine pathology evaluations.

Visit Breakdown

1. Informed consent will be obtained at the pre-operative surgery appointment.
2. Urine Pregnancy test (only for women of child bearing potential and only if a previous urine pregnancy exam has not been performed within 28 days of consent as standard of care)
3. Injection with the fluorescent dye will occur approximately 5 to 10 min. prior to ligation of the uterine vessels during the hysterectomy.

4. The uterus will be sent to pathology immediately after its removal where Woods lamp evaluation, measurement and photography will be performed.

d. **Prohibited Medications:** none

e. **Dose Limiting Criteria:** none

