12. DATA HANDLING AND RECORD KEEPING

- a. Registration Procedures:** After consent has occurred and eligibility criteria has been completed, subjects must be registered with the CCTO before enrollment to the study. Patients are registered by the Research staff calling the CCTO Office Monday through Friday, 8:00 AM - 4:30 PM. Prior to registration, eligibility criteria must be confirmed by the research staff.
- b. Confidentiality and De-Identification of Data:** Upon registration, the subject will be assigned a unique identifying code or number to which the subject will be identified by. All subject related materials will be identified by that subject's unique identifying code or number. Only the Research staff will have access to the code/number and information that identifies the subject in this study.
- c. Methods for Data Collection and Data Collection Tools:** Data will be entered into OpenClinica through electronic web-based case report forms (CRFs). OpenClinica is a secure open source system for electronic data capture and clinical data management. Data will be stored electronically on encrypted computers. Data collection from this study will be limited to the pathological findings at the time of endometrial cancer staging.
- d. Storage of Study Related Items :** This study's documents will be retained for a minimum of three years after study completion.

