14. STATISTICAL CONSIDERATIONS

- a. Sample Size and Study Duration:** 100 subjects will be entered into this pilot study. It is estimated that this study will be completed in less than one year.

- b. Study Endpoints:** Invasion depth as determined using each of three methods: Systemic Fluorescein Injection (SFI), Frozen Section (FS), and Permanent Section (PS).
- c. Data Analysis Plan:** The primary objective is basically to determine whether the SFI method works. Provided that it works, the analysis plan in support of the Secondary Objective is as follows: For each study subject, the paired difference in invasion depths determined using the SFI versus FS methods will be calculated and expressed as a percentage of the FS-based invasion depth. Likewise, the paired difference in invasion depths determined using the SFI versus PS methods will be calculated and expressed as a percentage of the PS-based invasion depth. Each type of paired difference will be summarized as the mean and standard deviation. Because PS is considered the definitive “gold standard” of determining invasion depth, the mean of the paired differences between SFI and PS methods will be compared against equivalence limits of -25% and $+25\%$ via the Two One-Sided Tests (TOST) procedure using an $\alpha=0.10$ significance level. If this mean is significantly “in between” both equivalence limits, then this will indicate that the discrepancy in invasion depths between SFI and PS is significantly less than 25% , and we will accordingly consider further investigation of the SFI method of determining invasion depth.

Sample Size and Power: When two methods are equivalent, the mean of their paired difference will be 0% . The power of the TOST procedure to declare that a mean of 0% is significantly “in between” equivalence limits of -25% and $+25\%$ depends heavily on the standard deviation of the paired difference when the sample size is fixed at 20 subjects. A simulation study using 1,000,000 simulations in PASS 12 software indicates that 20 subjects gives the TOST procedure $>90\%$ power at 10% alpha to declare a mean of 0% to be significantly “in between” the above-stated equivalence limits provided that the standard deviation of the paired differences is less than 37% . This power calculation shows that, if SFI agrees well with PS, then 20 subjects should provide our study with sufficient power to demonstrate that fact.

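### The permanent-section depth, which is the reference in the equivalence test, is not protected from knowledge of the fluorescein depth read earlier on the same area

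*Combined protocol and SAP*

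**What the plan says.** Section 9a fixes the order of the readings. The pathologist cuts into the most suspicious area, the cut surface is photographed under the lamp, and the SFI depth is read there from how the tissue looks in that light. Next, "The area that was measured and photographed will then be prepared for a frozen section to document depth of invasion". Then, "This same area will undergo histologic confirmation by permanent pathology to determine depth of invasion".

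On who does this, Section 9c says only: "The study pathologist will be informed when to expect a subject specimen and will prepare the lab for Woods lamp evaluation, measurement and photography". It does not say who reads the frozen section (FS) or the PS. Section 13 retains the photographs for comparison. The only coding described is in Section 12b, "All subject related materials will be identified by that subject's unique identifying code or number", and its purpose is confidentiality.

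Section 14c treats PS as the "definitive “gold standard” of determining invasion depth, the mean of the paired differences between SFI and PS methods" being what the two one-sided tests (TOST) examine. Each difference is "calculated and expressed as a percentage of the PS-based invasion depth". SFI versus FS is summarised by mean and SD and is not tested.

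**The concern.** SFI is always read first, so knowledge can pass only from SFI into the later histologic readings. That order protects the SFI value; it does nothing for the reference. A PS reader who has seen the SFI depth or the photograph may settle a doubtful invasion front nearer to it.

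In a test for a difference, a pull toward agreement would be conservative. In an equivalence test it works the other way. The mean of SFI minus PS moves toward zero and its spread probably narrows, and both make success easier. A method whose true mean discrepancy lies at or beyond the 25% limit could then pass the plan's only formal test, and passing is the stated ground for considering further work on SFI.

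**Working it through.** **Inputs from Section 14c.** Limits of 25% either way; alpha 0.10, applied to each one-sided test; SD of the paired percentage differences 37%; 20 subjects in the power text; 100 subjects planned.

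**The plan's own figure.** TOST succeeds when mean + t·s/√n < 25 and mean − t·s/√n > −25, with t the 90th percentile on n−1 degrees of freedom. For n = 20 and SD 37 the standard error is 37/√20 = 8.27. The normal approximation is 2Φ(25/8.27 − 1.282) − 1 = 91.8%. Exact integration over the sample SD gives 90.6%, and 88.9% at SD 38. The stated power above 90% for SD below 37% therefore reproduces. With 0.05 per side it would be 79.5%, so 0.10 per side is the reading intended.

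**Model for the risk (an assumption).** Let the recorded reference be PS* = PS + k(SFI − PS), where k is the fraction of the way PS moves toward SFI. Then SFI − PS* = (1 − k)(SFI − PS). With the denominator held at the true PS, the mean and SD of the percentage difference are both multiplied by (1 − k). The documents give no value for k, so a range is shown.

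**One case by hand.** n = 100, true mean 30%, k = 0.2. The mean becomes 24, the SD 29.6 and the standard error 2.96. With t = 1.290, success needs a sample mean below 25 − 1.290 × 2.96 = 21.18. The chance is about Φ((21.18 − 24)/2.96) = Φ(−0.95) = 17%, and exact integration also gives 17%.

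**Chance of declaring equivalence, exact integration**

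| True mean | N | k = 0 | k = 0.1 | k = 0.2 | k = 0.3 |
|---|---|---|---|---|---|
| 25% | 20 | 10% | 17% | 29% | 49% |
| 25% | 100 | 10% | 30% | 66% | 95% |
| 30% | 20 | 3% | 6% | 13% | 27% |
| 30% | 100 | 0.4% | 3% | 17% | 60% |
| 40% | 20 | 0.1% | 0.3% | 1% | 4% |
| 40% | 100 | 0% | 0% | 0% | 0.7% |

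**Sensitivity to the model.**

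- Only the mean shrinks and the SD stays at 37%: at N = 100 and a true mean of 25% the row becomes 10%, 27%, 53%, 77%. At 30% and k = 0.3 the chance falls from 60% to 42%.
- The denominator moves with PS, so that each difference d becomes (1 − k)d/(1 + kd) (simulation, 20,000 runs per setting, d floored at −95%). At a true mean of +25%, k = 0.1 to 0.3 gives 23% to 81% at N = 20 and 51% to 100% at N = 100. At −25% it gives 13% to 22% and 17% to 38%, from starting values of 11% and 12%. At +40% and k = 0.3 it gives 17% and 37%, well above the table.

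The direction is the same in every version. The size is not stable.

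**The case against.** The strongest reply is that this argues from silence. Sections 9a and 9c speak of the pathologist and the study pathologist without saying who reads FS or PS, or that the SFI depth is passed on. A reader might infer that one person makes all three readings with full knowledge of the earlier ones. The documents do not support that; they support only that no protection is specified. This part of the objection stands and sets the strength of the point.

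A reader might also take the shared area as the defect. It is not. Reading all three methods at one place is what makes the differences paired and interpretable.

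The figures depend on an assumed k, and k = 0.3 is a large shift for a histologic reading toward a gross visual estimate. With the denominator fixed, a method 40% out is almost never passed; the moving-denominator check weakens that reassurance for over-reading by SFI. Either way, no row of the table is an estimate of this trial's error rate.

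The stakes are also limited. The TOST serves the secondary objective of a pilot, and success leads only to considering further investigation. That bears on priority. It does not remove the gap, because the primary objective has no numerical criterion and the TOST is the plan's only formal test.

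Finally, FS is part of routine intraoperative care, and masking it could be impractical. Agreed: FS does not enter the TOST, so it could affect the test only by carrying over into PS. Masking FS is not asked for.

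**Conclusion.** The point holds as a risk of bias from an omission. SFI is read first, PS is read later on the same area, and nothing keeps the SFI value or photograph from the PS reader, while the test rewards agreement between the two. Whether PS would in fact be influenced, and by how much, cannot be learned from the documents, so it would be wrong to conclude that the result will be biased.

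If PS did move toward SFI, the error would favour declaring equivalence. Under the simple shrinkage model it matters most when the true discrepancy is near the 25% limit, and there the planned 100 subjects make a biased mean more certain to pass than 20 would. These statements rest on an assumed k, an SD of 37% and a fixed denominator. The change is worth making because it is cheap and because a PS reading made with knowledge of SFI cannot readily be repaired afterwards.

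**What to change.** In Sections 9a and 9c:

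1. Write down the SFI depth, with time and signature, when it is measured and before histology. A paper entry is enough, so the intraoperative result is not delayed.
2. Keep the SFI value and the Woods-lamp photograph off the permanent-section paperwork.
3. Record the PS depth from the slides before the SFI value or photograph is consulted.
4. Where routine sign-out already allows it, have PS read by someone other than the SFI reader, without requiring an added reader.
5. Record on the CRF whether the PS reader knew the SFI value, and report it with the results.

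The cost is protocol wording, one CRF item and a little discipline in the pathology workflow. One limit remains: where a single pathologist makes all the readings, memory of the SFI value may persist, and item 5 is there so that this can be seen.

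### SFI, frozen section and the gold standard are all read on one selected area, so the analysis cannot show whether SFI misses deeper invasion elsewhere in the uterus

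*Combined protocol and SAP*

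**What the plan says.** Section 9a fixes the order of events. After opening the uterus, the pathologist selects the site: "He or she will then cut into the myometrium in an area most suspicious for invasion". The cross section is photographed under the Woods lamp and SFI depth is measured on it. Frozen section comes next: "The area that was measured and photographed will then be prepared for a frozen section to document depth of invasion". The permanent section is then tied to that place: "This same area will undergo histologic confirmation by permanent pathology to determine depth of invasion".

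Section 14b lists the endpoints: "Invasion depth as determined using each of three methods: Systemic Fluorescein Injection (SFI), Frozen Section (FS), and Permanent Section (PS"). It gives no site for the permanent section and no maximum or whole-uterus depth. Section 14c calls permanent section the gold standard and tests the mean SFI-minus-PS percentage difference against limits of -25% and +25%.

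The secondary objective (Sections 3 and 6) and the schema (Section 4) name a different comparator, final pathology: "Comparison of final pathology depth of invasion with frozen section depth of invasion". That term is neither defined nor linked to permanent section. Section 9c sends the remaining specimens to routine pathology, and no study depth is taken from them.

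Section 5 states why depth matters: "Intraoperative evaluation of the depth of invasion of the cancer is critical, therefore, in determining which patients require lymphadenectomy".

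**The concern.** All three readings share one choice of site. If the deepest invasion lies elsewhere, SFI, frozen section and permanent section miss it together, and the miss drops out of both SFI minus FS and SFI minus PS. The omitted error has one direction: the maximum depth in the uterus cannot be less than the depth in the sampled area, so leaving it out can only hide understatement.

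Reading all methods at the same site is the right way to isolate measurement error. The difficulty is that it is the only reference, while the use described in Section 5 concerns the patient rather than one slice. The trial could report close agreement, and a reader could take this as evidence that SFI finds the depth on which the lymphadenectomy decision depends. The planned analysis has no means of confirming or refuting that.

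**Working it through.** **1. The plan's own figure.** Inputs from Section 14c: n = 20, limits ±25%, true mean 0%, SD 37%, alpha 0.10 in each one-sided test. Exact paired TOST power is 0.906, and at SD 38% it is 0.889. The stated power above 90% for SD below 37% is reproduced. This point does not affect it.

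**2. What the SFI-minus-PS difference contains.** Let A be the true depth at the measured area, M the maximum depth in the uterus (M ≥ A), and S the SFI reading.
- Planned difference: (S − A)/A. M does not appear.
- Difference relevant to the use in Section 5: (S − M)/M.
- If S = A in every woman, the planned difference is 0% whatever M is.

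**3. Sensitivity for invasion of 50% or more.** Let g be the fraction of women with 50% or more somewhere in the uterus who have less than 50% at the measured area. An SFI reading accurate at the site classes those women as below 50%, so whole-uterus sensitivity ≤ 1 − g. The documents give no value of g; these are assumptions.

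| g (assumed) | Whole-uterus sensitivity, at most | Same-area sensitivity could be |
|---|---|---|
| 10% | 1 − 0.10 = 90% | 100% |
| 20% | 1 − 0.20 = 80% | 100% |
| 40% | 1 − 0.40 = 60% | 100% |

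The fraction that matters is g, not the fraction whose deepest point lies outside the area. A woman with 60% invasion at the site and 80% elsewhere is still classed correctly.

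**4. Effect on the mean.** Assume SFI is unbiased at the site with SD 37%, and that in a fraction f of women M = kA. The mean difference against M is f(1/k − 1). For k = 2 and f = 10%, this is 0.10 × (0.5 − 1) = −5%. The probability that TOST declares equivalence against M, from 40,000 simulated trials per case with k = 2, is:

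| f (assumed) | Mean difference against M | n = 20 | n = 100 |
|---|---|---|---|
| 10% | −5% | 0.82 | 1.00 |
| 20% | −10% | 0.64 | 0.995 |
| 30% | −15% | 0.41 | 0.89 |

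With k = 1.5, f of 10% to 30% gives means of −3.3% to −10%, and probabilities of 0.88 to 0.68 at n = 20. Both sizes are shown because Section 14c computes power for 20 while Section 14a enrols 100.

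Against same-area PS the mean stays at 0% for every f. At n = 100, even a TOST against M would usually pass with 20% to 30% of women understated by half. Changing the reference in the mean test is therefore not enough; a patient-level table is needed.

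**The case against.** The strongest reply is that this is a pilot. Section 14c asks whether the method works, and success leads only to considering further investigation. Sections 5 and 11 put lymphadenectomy guidance in conditional, future terms. Same-area reading is the cleanest test of the dye boundary. Frozen section, which SFI might replace, uses the same site as routine care and would miss the same foci. All of this stands. It is why same-area PS should remain the main comparator, and why any shortfall should be reported for frozen section as well as SFI.

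A reader might infer three stronger points that the documents do not support.
- *That the objective and schema promise a whole-uterus comparison which the methods then break.* Final pathology is undefined and may simply mean permanent as opposed to frozen section. The terms are unreconciled; there is no explicit contradiction.
- *That the protocol itself calls the choice of site unreliable.* The Section 5 remark, "Gross visualization is highly inaccurate", concerns judging depth, in contrast with frozen section. It does not address where to cut. The schema also lists lamp exposure before the photograph of a representative area, so the lamp may inform the choice.
- *That every woman whose deepest point lies outside the area is a missed case.* The 60% and 80% example shows otherwise.

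What the reply does not remove is that the analysis contains no measure of depth outside the sampled area.

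**Conclusion.** The point holds as a limit on what the analysis can show. It is not an error in the planned test. It rests on Section 9a, the only operational description of the permanent section, because Section 14 is silent on site. On that description the trial can establish measurement agreement at the sampled site and nothing about deeper invasion elsewhere.

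The size is unknown. The ceilings of 90%, 80% and 60% are illustrations, conditional on the assumed g and on an SFI reading that is accurate at the site. The mean shifts are likewise conditional on the assumed f and k. This is a worthwhile, inexpensive improvement; the planned comparison remains valid for its narrower question.

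**What to change.** - Keep same-area permanent section as the measurement-accuracy reference and the TOST comparator.
- Define permanent section and final pathology separately in Sections 4, 6, 9a and 14b.
- Add CRF fields for whole-uterus maximum depth and myometrial thickness at that point, from the routine final pathology report (assumed to give them), and for myometrial thickness at the SFI site. Without the last, SFI depth cannot be classed against 50%: the percentages in Section 14c are relative to the reference depth, not to muscle thickness.
- Add to Section 14c a descriptive secondary comparison of SFI, and of frozen section, with whole-uterus maximum depth. Include the less-than-50% versus 50%-or-more cross-table with exact confidence intervals. Precision will depend on the number of deep cases, which the documents do not forecast.
- State that the same-area result alone supports only a claim of measurement agreement at the sampled site.

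The cost is a few abstracted fields and one table, with no extra patients or procedures and no change to patient management. The reported accuracy may look less favourable.
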